# 15.5. Screening Records

A record must be kept of all patients considered for the study who sign informed consent and who began any screening procedures. The information should include the patient' initials, unique patient identification numbers, whether they passed or failed screening, and, if they failed, the reason for screen failure.

# 15.6. Clinical Laboratory Certification

A central clinical laboratory will be used to analyze all samples in this study, with the exception of the urine pregnancy test and ad hoc urine drug screens. The investigator must maintain, on file, written evidence that the central clinical laboratory to be used is certified under the Clinical Laboratory Improvement Act or equivalent certification (depending on local regulations). Further, the investigator will maintain a copy of the certification, the range of normal values, the effective dates for the ranges, and the units of measurement for all laboratory tests requested in the protocol. If any of the laboratory measurements will be transformed and/or categorized in any way, a description of the procedures(s) used should be included. The investigator is expected to receive these documents before the shipment of clinical supplies.

# 15.7. Site Monitoring and Tonix's Right to Review Records

Monitoring and auditing procedures developed by Tonix and/or its designee will be implemented to ensure compliance with FDA and ICH GCP and GLP guidelines.

Tonix's designated representative (the monitor or auditor) will contact the investigator and conduct regular visits to the clinical site. The monitor will be expected and allowed to verify the investigator's qualifications, to inspect clinical site facilities, and to inspect study records, including proof of EC/IRB review, with the stipulation that patient confidentiality will be maintained in accordance with local and federal regulations, including HIPAA requirements. The monitor will also be responsible for confirming adherence to the study protocol, inspecting CRFs and source documents, and ensuring the integrity of the data. CRFs will be checked for accuracy, completeness, and clarity and will be cross-checked for consistency with source documents, including laboratory test reports and other patient records. Instances of missing or uninterpretable data will be resolved in coordination with the investigator.

The monitor/auditor will also investigate any questions concerning adherence to regulatory requirements. Any administrative concerns will be clarified and followed. The monitor will maintain contact with the site through frequent direct communications with the study site by email, telephone, facsimile, and mail. The investigator and all other site personnel agree to cooperate fully with the monitor and will work in good faith with the monitor to resolve any and all questions raised and difficulties detected by the monitor.

# 15.8. Audits and Inspections

The investigator understands that regulatory authorities, the EC/IRB, and/or Tonix or their designees have the right to access all CRFs, source documents, and other study documentation for on-site audit or inspection and will retain this right from the start of the study to at least 2 years after the last approval of a marketing application or for at least 2 years after clinical development of the study drug for the indication being studied has been discontinued. The investigator is required to guarantee access to these documents and to cooperate with and support such audits and inspections.

# 16. CONFIDENTIALITY

# **16.1.** Protection of Patient Anonymity

The investigator must make sure that each patient's anonymity is maintained. On CRFs or other documents submitted to Tonix or its agent, patient should not be identified by their names, but rather by their initials and the assigned study identification numbers. The investigator should keep a separate record of the patient initials, randomization codes, patient names, address, and contact information. Documents that contain the names associated with these initials and codes are not for submission to Tonix or its agents (e.g., written informed consent forms). These records should be maintained by the investigator in strict confidence except to the extent necessary to allow auditing by regulatory authorities, Tonix, or its agents. These records should be kept in compliance with HIPAA regulations.

Special Provisions for Confidentiality: In addition, a Certificate of Confidentiality (CoC) has been obtained from the FDA for the investigators to protect patients enrolled in the study. Investigators can use the Certificate to avoid being compelled to make "involuntary disclosure" (e.g., subpoenas, insurers, employers, or other third parties) of names and other identifying information about any individual who participates as a research patient (i.e., about whom the investigator maintains identifying information) during any time the Certificate is in effect.

# 16.2. Confidentiality of Study Information

All information relevant to this study, whether supplied by Tonix or its agents to the investigator or collected by the investigator in support of this study, is privileged and confidential. The investigator agrees to use this information to carry out the study and will not use it for other purposes without written consent from Tonix. It is understood that the investigator is under obligation to provide Tonix with all data obtained during the study. The information obtained from this study will be used by Tonix towards the clinical development of the indicated investigational drug and may be disclosed by Tonix to regulatory authorities, other investigators, corporate partners, or consultants as required.

### 16.3. Publication of Data and Protection of Trade Secrets

No presentations, abstracts (including meeting abstracts), or other publications based on the conduct or results of this study will be permitted without the express written permission of Tonix or its designated agent. All such presentations or publications will proceed only as collaborations between Tonix and the investigators.

If the investigator wishes to publish the results of this study, a copy of the proposed manuscript or abstract (including meeting abstracts) will be provided to Tonix or its designee for review, revision, and approval at least sixty (60) days before the expected date of submission for publication, unless otherwise arranged with Tonix in writing. This will enable Tonix to protect its proprietary information and augment the publication with insights or information of which the investigator may not be aware.

Patient names and other identifiers, such as photographs or audio or video recordings, may not be disclosed in any publication or public forum without prior written authorization from the

patients involved or their legal guardians. Tonix retains authority to delete any of its confidential information from such disclosures.

### **18.** APPENDICES

### APPENDIX 1. STUDY DESIGN AND SCHEDULE OF ASSESSMENTS

Period	Baseline	Phone f	Clinic Visits				
Visit	1	2	3	4	5	6	7 j
Study Week	0	2	7	16	28	40	52
Study Day	0	14 ± 3	49 ± 7	112 ± 7	196 ± 7	280 ± 7	$365 \pm 7$
Informed Consent	X						
Inclusion Criteria	X						
Concomitant Medications b	X	Xf	X	X	X	X	X
Vital Signs and weight	Xa		X	X	X	X	X
Inspection of oral cavity c	Xa				X	X i	X
Pregnancy Test d	Xa		X	X	X	X	X
Clinical Laboratory Assessments	Xa				X	X i	X
BDI-II	Xa		X	X	X	X	X
C-SSRS	Xa	X f	X	X	X	X	X
CGI-I (compared to P306 baseline only) e			X	X	X	X	X
PROMIS-Sleep (short form)	Xa		X	X	X	X	X
SDS	Xa		X	X	X	X	X
PCL-S					$X^h$	X h	X
Pharmacogenomic blood draw (optional) g	*	*	*	*	*	*	*
Adverse Events	X	X f	X	X	X	X	X
Telephone Visit		$X^{f}$					
Dispense Study Drug	X		X	X	X	$\mathbf{X}^{\mathrm{j}}$	
Collect/ Count Study Drug Returned			X	X	X	X	X

**Abbreviations:** BDI-II = Beck Depression Inventory-II; C-SSRS = Columbia-Suicide Severity Rating Scales; CGI-I (Clinician Global Impression of Improvement); PROMIS = Patient Reported Outcomes Measurement Information System; SDS = Sheehan Disability Scale; PCL-S = PTSD Checklist-Specific Version

<sup>a These assessments are only to be conducted for patients entering the study from Track B, or Track A patients that roll over into P306 greater than 14 days after the final visit of the previous study.

<sup>b Medications that are ongoing at the end of the previous study will be recorded as such in this study.

<sup>c In addition to the regularly scheduled examination, a visual examination of the oral cavity should be done at any visit in which an oral adverse event has been reported.

<sup>d Women of child-bearing potential only.

<sup>e The CGI-I will be done only in comparison to the baseline visit of P306.

<sup>f Patients enrolled from the double-blind lead-in study, P301/HONOR, only will have the phone check-in.

\*/gThe blood draw for the pharmacogenomic assessment can be obtained at any study visit (including an early termination visit). It should only be obtained one time during the study. Separate written, signed informed consent will be required if the patient is to participate in the optional pharmacogenomic assessment.

h Visit 5(Week 28) will be the "baseline" for PCL-S because it will capture the vast majority of the patients who have enrolled from the start of P306. The mean change in PCL-S total score and PCL-S clusters scores from Visit 5 (Week 28) to Visit 6 (Week 40), and to Visit 7 for Track B patients, will detect any potential worsening in total PTSD score or symptoms clusters due to long-term treatment of TNX-102 SL in the final 12-weeks, and 24-weeks for Track B patients, of the study.

<sup>i Track A patients only.

<sup>j Track B patients only.

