## 6. INVESTIGATIONAL PLAN

## 6.1. Overall Study Design

This is a 40 to 52-week, multicenter, open-label extension study designed to establish long-term safety exposure and to examine the long-term effect with daily bedtime dosing of TNX-102 SL 5.6 mg (2 x 2.8mg tablets) in patients with PTSD. This study will be conducted at approximately 35 sites in the United States (US).

Patients who have either: (a) completed the double-blind lead-in study and complete, *or are active (at the time of study discontinuation)* in the 12-week open-label extension study, P303; or (b) are currently enrolled in the double-blind lead-in study (HONOR study) that has been discontinued due to results of an interim analysis, will be eligible. For Track A patients, this extension study consists of 5 in-clinic visits, including the Screening/Baseline visit and visits after 7, 16, 28 and 40 weeks of treatment (Visits 3-6). There will also be a telephone visit after two weeks of treatment (Visit 2) for patients enrolling from the double-blind lead-in study, P301/HONOR. The total treatment duration of this study will be 40 weeks for patients enrolled under Track A criteria, and 52 weeks for patients enrolled under Track B criteria. Therefore, the maximum total duration of continuous treatment with TNX-102 SL could be approximately 64 weeks for those patients assigned to TNX-102 SL in the lead-in HONOR study who then also completed the 12-week open-label extension study P303.

For patients enrolling from the open-label extension study, P303, there is no need to repeat assessments at Visit 1 for this study, if the patient enrolls and initiates study treatment within fourteen days of completing the 12-week open-label extension study P303. For patients who are active in the double-blind lead-in study, P301/HONOR, all Baseline procedures and assessments will be completed at Visit 1.

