## 9.1.2. Screening Overview

The first study visit, Visit 1, will be where the study is explained to the prospective study patient, where written informed consent will be obtained and documented, and where protocol-specified study procedures and assessments will be completed.

For patients enrolling into this study from the 12-week open label extension study, P303, the P306 Baseline Visit (Visit 1) date is intended to be the same date as the final visit of the 12-week open label extension study, P303. However, if there are extenuating circumstances, Visit 1 of P306 may occur within fourteen days of their final visit in P303 without repeating baseline assessments. If more than fourteen days elapse between the final visit of P303 and start of the P306 study, medical monitor approval will be required and baseline assessments will need to be repeated.

For patients enrolling directly from the double-blind lead-in study, P301, all Visit 1 assessments will be performed. These patients are also expected to enter the P306 study at the same time as their final P301 visit; however, if there are extenuating circumstances, then Visit 1 of P306 may occur within fourteen days of their final P301 visit.

Once the patient has provided written informed consent to participate and has met all relevant inclusion criteria, this patient is eligible to begin the open-label treatment period, starting at bedtime on the day of enrollment. The patient should be dispensed three bottles of TNX-102 SL tablets, along with dosing and storage instructions. The end-of-study information collected at the final visit of the 12-week open label extension study P303, or the Visit 1 assessments completed as part of this protocol, will be considered the baseline values for Study P306.

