## 10.4.1.1. Columbia-Suicide Severity Rating Scale (C-SSRS)

The C-SSRS is a clinician-administered interview developed by researchers at Columbia University to assess suicide risk and to track suicidal ideation and behavior during clinical trials. This scale is intended to be administered by individuals who have received training in its administration. The questions contained in the Columbia-Suicide Severity Rating Scale are suggested probes. Ultimately, the determination of the presence of suicidal ideation or behavior depends on the judgment of the individual administering the scale.

The "since last visit" version of the C-SSRS will be completed at all study visits. Note that if there has been a significant change in responses to this scale indicative of increased suicide risk, appropriate intervention should be prescribed Section 10.4.1.2 and an AE should be recorded. The patient's response to BDI-II item 9 (suicidal ideation) should be reviewed prior to conducting the C-SSRS at the in-clinic visits to ensure the patient's responses are consistent between the BDI and the C-SSRS (and/or the reason for any inconsistency documented in the patient's chart).

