## 10.4.1.2. Safety Planning Intervention (SPI)

The C-SSRS is completed at every visit in order to assess for changes in suicidality during the study. If a patient scores a 4 or 5 on the Suicidal Ideation section of the C-SSRS at a clinic visit following enrollment, the patient should be withdrawn from the study and referred for appropriate emergency care. A score of 4 or 5 should also result in the reporting of a SAE.

If a patient scores a 2 or 3 on the Suicidal Ideation section of the C-SSRS at any visit, the investigator should consider the implementation of a Safety Planning Intervention (SPI). The recommended SPI for this study is the plan developed by [name] and [name] which has been adopted by the US Veteran's Administration (VA) (Stanley & Brown, 2012). The VA SPI is a brief clinical intervention aimed at mitigating suicide risk. It consists of a written, prioritized list of coping strategies and sources of support that patients can use to alleviate a suicidal crisis. Sites may use an internally-developed SPI if similar in scope and purpose to the VA SPI.

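### Track A patients who start P306 1 to 14 days after their P303 final visit are given 120 tablets without a Visit 1 C-SSRS or BDI-II, and the text conflicts for P303 patients placed in Track B

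*Protocol*

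**What the plan says.** The waiver appears in four places in the protocol.

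- Section 6.1, for those coming out of the 12-week extension: "there is no need to repeat assessments at Visit 1 for this study, if the patient enrolls and initiates study treatment within fourteen days", counted from the end of P303.
- Section 9.1.2: Visit 1 is meant to fall on the day of the P303 final visit, but "if there are extenuating circumstances, Visit 1 of P306 may occur within fourteen days of their final visit in P303 without repeating baseline assessments".
- Section 9.1.5: the BDI-II and C-SSRS are listed only for direct P301 entrants and for P303 entrants past 14 days. They are not in the list for all patients.
- Appendix 1, footnote a, attached to both instruments at Visit 1: "These assessments are only to be conducted for patients entering the study from Track B, or Track A patients that roll over into P306" after more than 14 days.

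The sections on the instrument read differently. Section 10.4.1.1 says that the since-last-visit "version of the C-SSRS will be completed at all study visits". Section 10.4.1.2 says: "The C-SSRS is completed at every visit in order to assess for changes in suicidality during the study". Neither states an exception. Sections 10.4.1.3 and 10.4.1.5, by contrast, expressly let the Week 12 visit of the 12-week study stand in for Visit 1 for the oral examination and laboratory tests.

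Every patient receives three bottles of 40 tablets at Visit 1 (section 8.1). The Week 2 call, with its C-SSRS, is only for direct P301 entrants (section 9.2; Appendix 1, footnote f).

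**The concern.** A score taken at the P303 final visit cannot describe the days after it. If Visit 1 is later, the gap days are unscored when the drug is handed over. Every other scheduled dispensing visit has a C-SSRS on the same day.

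The waiver removes two things at Visit 1. One is the prompt in section 10.4.1.2 that starts "If a patient scores a 2 or 3 on the Suicidal Ideation section of the C-SSRS at any visit", when the investigator is to consider a Safety Planning Intervention. The other is any scored information, including BDI-II item 9, on whether ideation has risen since P303 ended. Inclusion criterion 4 does not fill the gap, because it is worded around the lead-in and 12-week studies rather than the time up to Visit 1. The package insert in Appendix 3, for another formulation of the same active ingredient, warns that overdose can, rarely, be fatal.

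Sites also face instructions that cannot all be followed.

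**Working it through.** **1. Who is covered by which text.** The synopsis puts P303 patients who had active drug in P301 in Track A, and patients active in P303 who had placebo in P301 in Track B. SAP section 3 simply labels P303 entrants Track A. For a P303 entrant with a gap of 1 to 14 days:

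| Source | Track A | Track B (P303-active, placebo in P301) |
|---|---|---|
| 6.1, 9.1.2, 9.1.5 | waived | waived |
| Appendix 1, footnote a | waived | required |
| 10.4.1.1, 10.4.1.2 (C-SSRS) | required | required |

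The four waiver texts agree only for Track A.

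**2. Supply at Visit 1.** Inputs: 3 bottles, 40 tablets each (8.1), 2 tablets a night.

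- 3 × 40 = 120 tablets; 120 / 2 = 60 nights. Dosing to Day 49 needs 49 × 2 = 98 tablets.
- Later visits: 4 × 40 = 160 at Week 7 and 5 × 40 = 200 at Weeks 16 and 28, each with a scheduled C-SSRS.
- Track A dispensing visits are 1, 3, 4 and 5. For a gap patient, 1 of these 4 has no C-SSRS.

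**3. Time to the next C-SSRS.** Days from the P303 final visit to Visit 3 = gap + 49, with a window of ± 7 days (Appendix 1).

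| Gap | At target | With window |
|---|---|---|
| 0 (same day) | 49 | 42 to 56 |
| 1 day | 1 + 49 = 50 | 43 to 57 |
| 14 days | 14 + 49 = 63 | 56 to 70 |

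The range for gap patients is 43 to 70 days. Planned spacing elsewhere is 112 − 49 = 63 days (Visits 3 to 4), 196 − 112 = 84 days (Visits 4 to 5) and 280 − 196 = 84 days (Visits 5 to 6). The length is therefore not unusual. What is missing is the check before dispensing.

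**4. Does Week 7 recover the gap days?** It depends on what counts as the last visit. If that is Visit 1, the gap days are never scored. If it is the P303 final visit, they are scored, but only after 42 to 56 days in P306. The protocol does not say which.

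**5. Is entry still open?** Completion was estimated for September 2019 (synopsis). A 40-week patient finishing on 30 September 2019 would have entered 280 days earlier, on 24 December 2018. That is before Amendment 4 of 5 June 2019, the version that the SAP cites. The SAP reference list also contains a 2023 source. Entry has probably closed.

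**The case against.** The strongest reply is that the waiver is deliberate and specific. The visit instructions in 6.1, 9.1.2 and 9.1.5 tell a site exactly what to do, and SAP section 3 repeats the waiver. Sections 10.4.1.1 and 10.4.1.2 describe an instrument in general terms, and specific text normally governs. This softens the conflict for Track A, but it neither settles the Track B subgroup nor supplies information about the gap days.

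Other checks do remain. The investigator interviews the patient for suitability (7.1), confirms that the patient is still satisfactory for the extension (10.1), and reviews new adverse events (9.1.5). A reader might infer that nobody asks about the gap days at all, and that would be wrong. But the interview and adverse event review name no suicidality instrument. The adverse event review opens with general, non-leading questions (10.4.1), and the screening scores available for these patients are the P303 final-visit values.

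A reader might also argue from direct P301 entrants, who may have a gap of up to fourteen days too, yet for whom the rule is: "For patients enrolling directly from the double-blind lead-in study, P301, all Visit 1 assessments will be performed". The documents do not support that as evidence of inconsistent standards. Under the synopsis, Visit 1 for patients from the discontinued P301 study replaces their early termination visit, so it also serves as their closing assessment.

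The objection that few patients are involved stands: a gap is allowed only for exceptional reasons.

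**Conclusion.** The point holds as a limited safety gap that is cheap to close. Track A P303 entrants with a gap of 1 to 14 days receive 120 tablets without a structured suicidality check of those days, and their next scheduled C-SSRS is at Week 7. For P303-active patients who had placebo in P301, the texts contradict each other.

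Three stronger readings are not supported:

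- That all P303 entrants lose the assessments under footnote a. It is drawn by track and, read literally, requires them for Track B.
- That the waiver delays the withdrawal rule. That rule begins "If a patient scores a 4 or 5 on the Suicidal Ideation section of the C-SSRS at a clinic visit following enrollment", so it first acts at the Week 7 clinic visit with or without a Visit 1 score.
- That the usual rollover is unsafe. On the same day nothing is lost, assuming the P303 final visit included a C-SSRS. The use of its data as baseline (9.1.2) implies this, but the P303 schedule is not in the documents.

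The number of gap patients is not stated and is probably small. No sample size or power figure is affected.

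**What to change.** 1. In footnote a and sections 6.1, 9.1.2 and 9.1.5: for any P303 entrant, of either track, whose Visit 1 is later than the P303 final-visit date, do the BDI-II and then the since-last-visit C-SSRS, looking back to the P303 final visit, before dispensing. This also removes the Track B contradiction. The longest interval between C-SSRS checks up to Visit 3 falls from 14 + 56 = 70 days to 56 days.
2. In 10.4.1.1 and 10.4.1.2: state that for same-day rollover the P303 final-visit C-SSRS counts as the Visit 1 record.
3. Extend inclusion criterion 4 (section 7.2 and synopsis) to the period up to Visit 1. A new score cut-off for eligibility is not needed.
4. In SAP section 7.1: for entrants within 14 days, keep the P303 final-visit BDI-II as the baseline for change scores. Otherwise the rule of taking the last value before the first P306 dose would move the baseline for gap patients only, and BDI-II change is both an MMRM endpoint (SAP 9.1.1) and a safety endpoint (SAP 2.2.2).

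The cost is one questionnaire and one brief interview for the few gap patients, with instruments and raters already in the study, plus short text edits. If entry has closed, apply the protocol wording to any later extension with the same rollover rule, and add a listing of gap patients with gap length and Week 7 C-SSRS result.
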